## 8.6 Efficacy

CR rate will be summarized for the safety and EE subjects as the proportion (%) of subjects with CR. In addition to presenting the CR rate, its associated exact 95% CI for each treatment arm will also be presented.

DOR is defined as the time from the date when criteria for response are met to the date of PD or death due to any cause, whichever occurs first. Subjects alive with no PD will have their DOR censored at the date of the last clinical assessment. The DOOR will be summarized in each treatment arm by providing the median DOR together with associated 95% CI, using Kaplan-Meier methodology.

Overall response will be summarized in number (%) of subjects in each category of responses (CR, PR, mCR with HI, mCR without HI, HI). ORR will be analyzed by using the similar method as primary endpoint CR. DOR, as defined above, will also be evaluated in regard to ORR. Time to AML is calculated from first day of study treatment to first onset of AML. Kaplan-Meier methodology will be utilized. Rate of AML transformation will be analyzed by using the similar method as primary endpoint CR.

Survival data are collected at treatment and follow-up periods. Subjects will be followed until death or withdrawal of consent from the study, whichever occurs first.

OS is defined as the number of days from the first day of treatment to the date of death due to any cause. Kaplan-Meier methodology will be utilized.

RFS is defined as the time from the date of randomization to disease relapse or death, whichever occurs first. If neither event occurs, RFS will be censored at the date of the last clinical assessment. Kaplan-Meier methodology will be utilized.

Time to AML, OS and RFS will be analyzed using the similar methods as DOR.

Transition rate to HSCT will be analyzed using the similar methods as CR.

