## 2.0 BACKGROUND INFORMATION

### 2.1 Disease Background

Myelodysplastic syndromes (MDS) are a heterogeneous group of neoplasms arising from a clonal hematopoietic precursor. MDS is characterized clinically by cytopenia and a tendency to transform to acute myeloid leukemia (AML). Prognostic scoring systems have been developed to help stratify patients based on predicted survival and progression to AML. In practice, treatment decisions are made by grouping patients with MDS into lower and higher risk subgroups as defined by clinical prognostic scoring systems. Specifically, the International Prognostic Scoring System (IPSS) and its more modern version, the revised-IPSS (IPSS-R), represent the most widely used clinical prognostic tools. Those patients that fall in the higher risk group have an expected survival of less than 12 months if left untreated and progress to AML greater than 30% of the time.

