Overall, *TP53*-mutant MDS and AML patients have a median OS ranging from 5-9 months with 8 months representing the best estimate when restricting to MDS and oligoblastic AML (20-30% blasts). Together, these data highlight the dismal outcomes of *TP53*-mutant MDS patients and the dire need for the development of novel therapeutic strategies, particularly in this patient population.

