### 8.3.2 Secondary

1. Rate of CR
2. DOCR, defined as the time from documentation of CR to disease relapse
3. DOR, defined as the time from documentation of tumor response to disease relapse/progression or death as a result of any cause
4. ORR is the proportion of subjects achieving HI, PR, CR, marrow CR by modified IWG 2006 criteria
5. Rate of and time to AML transformation, according to WHO criteria
6. OS

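### Time to AML: the plan uses Kaplan-Meier with AML onset as the only event, leaves the handling of death without AML unstated, and neither available reading estimates AML incidence

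*Combined protocol and SAP*

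**What the plan says.** Section 8.3.2 lists as a secondary endpoint "Rate of and time to AML transformation, according to WHO criteria". Two analyses follow from it.

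- **Time to AML.** Section 8.6 states: "Time to AML is calculated from first day of study treatment to first onset of AML. Kaplan-Meier methodology will be utilized". The synopsis (Efficacy Analyses) and section 7.2.3 say the same. Death is not named as an event, a competing event or a reason for censoring.
- **AML rate.** Section 8.6 states: "Rate of AML transformation will be analyzed by using the similar method as primary endpoint CR". In practice this is a simple proportion with an exact 95% confidence interval. Section 7.2.6 agrees.

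The synopsis and section 8.6 then add: "Time to AML, OS and RFS will be analyzed using the similar methods as DOR". In section 8.6, DOR runs "to the date of PD or death due to any cause, whichever occurs first", and its censoring rule is "Subjects alive with no PD will have their DOR censored at the date of the last clinical assessment". DOR is summarised by a Kaplan-Meier median with 95% CI.

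No competing-risk method appears anywhere in the document.

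Two background statements bear on how common death without AML will be. Section 2.2 gives TP53-mutant MDS and AML a "median OS ranging from 5-9 months with 8 months representing the best estimate". Section 2.1 says that untreated higher-risk patients "progress to AML greater than 30% of the time".

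**The concern.** A subject who dies without AML can no longer develop it. If that subject is censored, Kaplan-Meier proceeds as if AML could still occur later at the same rate as in those still alive. One minus the Kaplan-Meier estimate then describes AML risk in a hypothetical population where nobody dies first. It does not describe the proportion who transform. With median survival of about 8 months, deaths without AML will be frequent, so the difference is not negligible.

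If death is instead counted as an event, as it is for DOR, the estimate is internally sound but measures AML or death. Labelled as time to AML, it would be badly misread.

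What is at stake is the curve and median for one secondary endpoint. The analyst must choose between two incompatible readings, neither of which answers the stated question. The curve may also disagree visibly with the AML proportion in the same report.

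**Working it through.** **The plan's own figure.** The document states no AML incidence, event count or precision for this endpoint, so there is nothing to reproduce. The only design figure is the sample size in the synopsis: 6 × 6 + 10 = 46, which agrees.

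**Inputs**

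- Median overall survival (OS): 8 months, range 5 to 9 (section 2.2).
- Proportion ever transforming: 30%, varied from 20% to 40%. This is a proxy: section 2.1 gives more than 30% for untreated higher-risk MDS.
- Median survival after AML: 4 months, varied from 2 to 4. This is an assumption, not in the documents.
- Constant hazards throughout. This is also an assumption.

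**Model.** Let λ1 be the hazard of AML, λ2 the hazard of death without AML, λ = λ1 + λ2, and μ the hazard of death after AML. With p the proportion ever transforming, λ1 = pλ.

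- Overall survival: OS(t) = exp(−λt) + λ1[exp(−μt) − exp(−λt)]/(λ − μ)
- Cumulative incidence of AML: p[1 − exp(−λt)]
- One minus Kaplan-Meier, deaths censored: 1 − exp(−λ1t)
- AML or death: 1 − exp(−λt)

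**Base case.** μ = ln 2/4 = 0.1733. Solving OS(8) = 0.5 with p = 0.30 gives λ = 0.1102, λ1 = 0.0331 and λ2 = 0.0772 per month. Check: 0.414 alive without AML + 0.086 alive with AML = 0.500.

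| Month | Cumulative incidence | 1 − KM, deaths censored | Ratio |
|---|---|---|---|
| 6 | 14.5% | 18.0% | 1.24 |
| 12 | 22.0% | 32.8% | 1.49 |
| 24 | 27.9% | 54.8% | 1.97 |

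At 12 months, for example: 0.30 × [1 − exp(−0.1102 × 12)] = 0.220, against 1 − exp(−0.0331 × 12) = 0.328.

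**Median.** With deaths censored, the Kaplan-Meier median is ln 2/λ1, about 21.0 months. Only 30% ever transform in this model, so no true median time to AML exists.

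**Death counted as an event.** At 12 months, 1 − exp(−0.1102 × 12) is about 73%, and the median is ln 2/0.1102 = 6.3 months. That is AML-free survival, against a true AML incidence of 22.0%.

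**Sensitivity of the 12-month excess (deaths censored)**

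- Median OS 8 months, 20–40% transforming, post-AML median 2–4 months: 6.7 to 13.4 points.
- Median OS 5–9 months, other ranges as above: 5.5 points (18.1% against 12.6%) to 27.9 points (64.9% against 37.1%).

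**Check at the trial's size.** In 4,000 simulated trials of 46 subjects under the base case:

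- With follow-up of 6–24 months, the mean 12-month estimates were 32.8% (1 − KM) and 22.1% (Aalen-Johansen). The crude AML proportion averaged 23.4%.
- With follow-up of 12–36 months, the 24-month estimates were 54.3% and 27.7%. The crude proportion averaged 27.1%.

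The crude proportion is not inflated by this mechanism, although it takes no account of unequal follow-up.

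**The case against.** **The plan never says that deaths are censored.** This is correct, and a reader should not infer it as fact. Under DOR, only subjects alive and progression-free are censored, so the cross-reference permits the reading that death is an event. Against that, the same sentence covers OS and RFS, which keep their own event definitions, so it may import only the estimator and summary. Section 8.6 also names death for DOR and RFS but not for time to AML. The text does not settle the matter, and the defect is that it does not.

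**AML incidence as such is not overstated.** This stands. The AML rate is a separate crude proportion. The problem is confined to the time-to-AML curve and its median.

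**No landmark estimate is planned.** This also stands. Following DOR, the output would be a median with 95% CI. The 12- and 24-month contrasts show how far the curve departs from incidence; they are not figures the plan promises to report.

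**The inputs fit loosely.** The 30% is for untreated patients, while these subjects receive azacitidine. The 8 months includes disease with 20–30% blasts, while section 2.10 limits the trial to under 20%. Using 8 months directly as the median for death before AML would give a larger gap (23% against 36% at 12 months), but OS also includes deaths after AML. The calibration above avoids that error.

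**Comparability across dose levels.** A reader might infer that the Kaplan-Meier figures rise or fall with mortality alone, so that dose levels cannot be compared. That is not supported. Under constant independent hazards, 1 − exp(−λ1t) contains no death hazard. It is the cumulative incidence that depends on mortality. Nor does the plan specify any test between doses or historical comparison of AML.

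**Conclusion.** The point holds in this form: AML onset is the only defined event, Kaplan-Meier is the estimator, the handling of death without AML is unstated, and the two relevant sentences can conflict. If deaths are censored, the curve exceeds AML incidence whenever deaths without AML occur. The direction does not depend on the numerical assumptions, but the size does. The base case gives 32.8% against 22.0% at 12 months, and the 12-month excess runs from about 5.5 to 28 points over the ranges examined. If deaths are counted, the result is a valid AML-free survival estimate under the wrong name.

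Severity is low. This is a descriptive secondary endpoint in a phase 1 trial of up to 46 subjects. The RP2D rests on biological effect, exposure and dose-limiting toxicity, and the sample size on cohort counts.

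**What to change.** In the synopsis, section 7.2.3 and section 8.6:

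1. Name death without AML as a competing event for time to AML.
2. Report the Aalen-Johansen cumulative incidence of AML with 95% CI, for example at 6 and 12 months.
3. Censor subjects alive without AML at the last clinical assessment.
4. Remove time to AML from the sentence that applies the DOR methods.
5. If a Kaplan-Meier curve or median is wanted, report AML-free survival (AML or death) separately under that name.

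The cost is wording and a standard procedure, since dates of death are already collected for OS. One detail should be settled at the same time. Section 6.9 continues response assessments after treatment only for some subjects, so the text should say how to classify a death that occurs well after the last disease assessment.

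The downside is that no median time to AML can be quoted when fewer than half of subjects transform.

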	
cycle of APR-548 and who have at least one post-treatment clinical response assessment. The EE population will be the secondary analysis population for efficacy.
 
PK population: Subjects will be evaluable for PK if at least one sample for PK evaluation has been obtained.
 
Safety Analyses
 
Safety data including AEs, vital signs, laboratory data, electrocardiogram (ECG), ophthalmologic assessment findings, and other physical exam findings will be tabulated for the safety population. AEs will be tabulated by System Organ Class (SOC), preferred term, severity, and relationship to treatments. The tabulation of laboratory parameters will include the normal ranges for each parameter. Each value will be classified as falling above, below, or within the normal range. Laboratory parameters will also be tabulated by maximum NCI-CTCAE v5.0 severity grade.
 
Efficacy Analyses
 
CR rate will be summarized for the safety and EE subjects as the proportion (%) of subjects with CR. In addition to presenting the CR rate, its associated exact 95% confidence intervals (CI) for each treatment arm will also be presented.
 
DOR is defined as the time from the date when criteria for response are met to the date of relapse/PD or death due to any cause, whichever occurs first. Subjects alive with no relapse/PD will have their DOR censored at the date of the last clinical assessment. The DOOR will be summarized in each treatment arm by providing the median DOR together with associated 95% CI, using Kaplan-Meier methodology.
 
Overall response will be summarized in number (%) of subjects in each category of responses (CR, PR, marrow complete response [mCR] with HI, mCR without HI, HI). ORR will be analyzed by using the similar method as primary endpoint CR. DOR, as defined above, will also be evaluated in regard to ORR. Time to AML is calculated from first day of study treatment to first onset of AML. Kaplan-Meier methodology will be utilized. Rate of AML transformation will be analyzed by using the similar method as primary endpoint CR.
 
Survival data are collected at treatment and follow-up periods. Subjects will be followed until death or withdrawal of consent from the study, whichever occurs first.
 
OS is defined as the number of days from the first day of treatment to the date of death due to any cause. Kaplan-Meier methodology will be utilized.
 
RFS is defined as the time from the date of randomization to disease relapse or death, whichever occurs first. If neither event occurs, RFS will be censored at the date of the last clinical assessment. Kaplan-Meier methodology will be utilized.
 
Time to AML, OS and RFS will be analyzed using the similar methods as DOR.
 
Transition rate to HSCT will be analyzed using the similar methods as CR.

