## 4.0 TRIAL DESIGN

### 4.1 Overview of Trial Design

This is an open-label FIH phase 1 clinical trial that will assess safety, PK, and clinical activity of p.o. administered APR-548 in combination with azacitidine for the treatment of *TP53*-mutant MDS.

Treatment will be administered on an outpatient basis but may be administered in the inpatient setting for subjects who are hospitalized and meet criteria for study treatment. No investigational or commercial agents or therapies other than those described below may be administered with the intent to treat the subject's disease under study.

The study is guided by a 3+3 dose escalation of APR-548 in the safety run-in monotherapy and the safety run-in combination therapy portions.

APR-548 will initially be given p.o. QD during Days 1 – 4 of a 28-day safety run-in period. The first 3 subjects enrolled on each dose level will be evaluated for a 28-day DLT safety follow-up period prior to enrolling additional subjects on that dose level or prior to dose escalation. If no DLT is observed, subjects will proceed to the safety run-in combination therapy portion with APR-548 in combination with azacitidine administered s.c. or i.v. at the standard dose of 75 mg/m^2 on Days 1-7 of the 28-day cycle. The first 3 subjects on each dose level of the combination with APR-548 and azacitidine will be evaluated for a 28-day DLT safety follow-up period prior to enrolling additional subjects on that dose level or prior to dose escalation with the combination treatment.

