### 7.2.2 Duration of Response

DOR is defined as the time from the date when criteria for response are met to the date of PD or death due to any cause, whichever occurs first. Subjects alive with no PD will have their DOR censored at the date of the last clinical assessment. The DOOR will be summarized by providing the median DOR together with associated 95% CI, using Kaplan-Meier methodology.

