## 8.2 Analysis Populations

Safety population: Subjects will be evaluable for safety if they receive at least one dose of APR-548. The safety population will be the primary analysis population used for all analyses such as subject disposition, subject demographics, exposure, safety parameters and efficacy parameters. The safety population will be the primary analysis population for efficacy.

EE population: All subjects who complete at least one treatment cycle of APR-548 and who have at least one post-treatment clinical response assessment. The EE population will be the secondary analysis population for efficacy.

PK population: Subjects will be evaluable for PK if at least one sample for PK evaluation has been obtained.

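### RFS starts at a randomisation this trial does not have, DOR has two conflicting end rules, and the TI window runs from an undefined enrollment and does not match the TI objective

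*Combined protocol and SAP*

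**What the plan says.** **RFS.** The Synopsis (Efficacy Analyses), Section 7.2.5 and Section 8.6 give the same rule: "RFS is defined as the time from the date of randomization to disease relapse or death, whichever occurs first". Section 4.1 describes the design: "The study is guided by a 3+3 dose escalation of APR-548 in the safety run-in monotherapy and the safety run-in combination therapy portions". The other time-to-event endpoints in Section 8.6 have a usable origin: "OS is defined as the number of days from the first day of treatment to the date of death due to any cause" and "Time to AML is calculated from first day of study treatment to first onset of AML". Section 8.2 adds: "The safety population will be the primary analysis population for efficacy".

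**DOR.** In the Synopsis (Efficacy Analyses), DOR runs "to the date of relapse/PD or death due to any cause, whichever occurs first". The endpoint lists in the Synopsis and Section 8.3.2 also name relapse alongside progression and death. Sections 7.2.2 and 8.6 instead run DOR "to the date of PD or death due to any cause, whichever occurs first", and censor accordingly: "Subjects alive with no PD will have their DOR censored at the date of the last clinical assessment". The Synopsis censoring sentence names relapse as well as PD. Duration of CR (DOCR) is a separate endpoint in Section 8.3.2. It ends at relapse, and death is not mentioned.

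**TI.** Section 3.2 lists 8 weeks of RBC and/or platelet TI under the activity of the combination. The endpoint in the Synopsis and Section 8.3.2 is TI in the 8 weeks following enrollment, a term the protocol does not define. The Synopsis Treatment Plan puts a 28-day APR-548 monotherapy run-in before the combination.

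**The concern.** An endpoint definition should give every analysed subject one start date, one end rule and one censoring rule. RFS names a start date that no subject has. DOR has two end rules, so the result depends on which section the programmer follows. The TI window may lie partly or wholly before the treatment it is meant to evaluate. If these points stay open, they will be settled after responses, relapses and transfusions are known. The stake is the credibility of three descriptive summaries. No hypothesis test and no dose decision depends on them.

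**Working it through.** **Sample size.** The Synopsis gives 6 subjects in each of 6 escalation cohorts plus 10 at the RP2D: 6 × 6 + 10 = 46, which reproduces the plan's figure. The three endpoints have no power or event target, so the rest is a comparison of definitions plus calendar arithmetic.

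**Calendar.** Day 1 is the first APR-548 dose. The run-in takes 28 days and each cycle 28 days.
- Cycle 1 Day 1 = 28 + 1 = Day 29.
- Cycle 3 Day 1 = 28 + 56 + 1 = Day 85, the first scheduled on-combination disease assessment (±7 days, Table 12 footnotes).
- Cycle 5 Day 1 = 28 + 112 + 1 = Day 141; Cycle 5 Day 15 = Day 155.

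**RFS.** With no randomisation date, an origin must be substituted. A first-dose origin and a response origin differ by 85 − 1 = 84 days for a response first seen at Cycle 3 Day 1 (77 to 91 with the window). Appendix V defines relapse only after CR, PR or HI, so from a first-dose origin only death can be an RFS event in a non-responder. The text does not say this.

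The censoring rule matters too. Section 6.9 continues off-treatment response assessments for responders and for transplanted subjects in remission, whereas the Synopsis (Duration of Follow-Up) follows survival until death or withdrawal of consent. If the present rule (last clinical assessment) is kept with a first-dose origin, a non-responder's late death counts, but a living non-responder may be censored near the end of treatment. That biases the Kaplan-Meier curve downward.

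**DOR.** Appendix V, applied after CR or PR:

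| Finding | Relapse? | PD? |
|---|---|---|
| Granulocytes or platelets down by at least 50% from best response | yes | yes |
| Transfusion dependence | yes | yes |
| Isolated haemoglobin fall of 2 g/dL or more | yes | yes |
| Isolated haemoglobin fall of 1.5 to <2 g/dL | yes | no |
| After CR, blasts back to a pretreatment level of 5% or less | yes | no |

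For the last row, take 4% before treatment, CR at 2%, then a return to 4%. The return is relapse. It is not PD, because the band below 5% needs more than 5%. With exactly 5% before treatment, a return to 5% exceeds neither 5% nor 10%, so it is not PD whichever blast band applies. After HI, progression and relapse share one definition, so there is no gap.

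Illustration with assumed dates: response on Day 85, then an isolated haemoglobin fall of 1.6 g/dL on Day 141.
- Relapse/PD rule: 141 − 85 = 56 days.
- PD rule, PD found on Day 155: 155 − 85 = 70 days.
- PD rule, death on Day 244 with no PD recorded: 244 − 85 = 159 days.
- PD rule, alive with no PD: censored.

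For responders who stop treatment for another reason, Section 6.9 schedules response assessments only until relapse, so a later PD may never be recorded.

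**TI.** Suppose enrollment means study entry, k days before the first dose (k from 0 to 28, if it falls within the 28-day screening period). The window is 56 days, of which k are pre-dose and 28 are run-in. Combination days = 56 − 28 − k = 28 − k, so 28 at most and 0 at k = 28. The first 56 combination days are Days 29 to 84, so 8 weeks of TI on combination cannot be complete before Day 84.

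The share of subjects affected depends on cohort sizes and on whether the added RP2D subjects do the run-in:
- maximum plan, added subjects skip it: 36/46 = 78%;
- four levels of 6, plus 10 who skip it: 24/34 = 71%;
- four levels of 3, plus 10 who skip it: 12/22 = 55%;
- added subjects also do it: 100%.

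**The case against.** The intended meaning of RFS and DOR is easy to guess. The first day of treatment is the natural RFS origin, and the Synopsis and endpoint lists already carry the fuller DOR wording, so these are harmonisation edits. The 84 days compares two possible origins and is not an error in any result. Response can also be dated before Day 85, since HI rests on counts and transfusions and an optional Day 15 assessment exists. For DOR, several triggers are both relapse and PD, the documents give no frequency for relapse without PD, and the evaluation required whenever progression is suspected can shorten the gap on treatment. All of this stands as a limit on size. It does not supply an RFS date or reconcile the two DOR rules.

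On DOCR, the DOR paragraph follows CR rate, counts death, and is then said to apply to ORR too. This suggests death was meant to count for CR duration, but it is an inference.

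TI is the weakest limb. Section 4.1 speaks of enrolling further subjects at combination dose levels, and on that reading all 56 days could be on combination. The transfusion log in Table 12, which starts 8 weeks before enrollment, points to study entry without settling it. A reader might infer that TI on combination goes unmeasured in 78% of subjects. The documents do not support that: the term is undefined, part of the window may be on combination, and 36 of 46 holds only at the maximum plan if the added subjects skip the run-in. A reader might also infer that subjects never transfused at baseline will be counted as successes. The endpoint speaks of achieving TI and baseline transfusions are logged, so the missing baseline rule is an ambiguity and not a stated miscount.

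**Conclusion.** The point holds, with unequal strength across the three endpoints. RFS cannot be computed as written. DOR is contradictory: the same responder can have different durations, or be an event under one rule and censored under the other, at an unknown frequency. The TI objective and endpoint do not match if enrollment means study entry, which is the likelier reading; a run-in subject then has 0 to 28 of 56 window days on combination.

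A reader might take three faulty definitions as a sign that the main results are unsound. The documents do not support that. RFS, DOR and TI do not enter the definitions of CR rate, ORR, OS, DLTs or the RP2D, and all three are descriptive. The changes should be made before analysis, because they are cheap now and open to hindsight later.

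**What to change.** - **RFS** (Synopsis, 7.2.5, 8.6): start at the first day of treatment, as for OS and time to AML. State that relapse applies only to responders. Censor living non-responders at the date last known alive, and living responders without relapse at the last response assessment.
- **DOR** (7.2.2, 8.6): end at relapse/PD or death, and censor subjects alive with neither relapse nor PD, matching the Synopsis and Section 8.3.2. Apply the same death rule to DOCR.
- **TI** (Synopsis, 8.3.2): count at least 56 consecutive transfusion-free days starting on or after Cycle 1 Day 1 of the combination. Report the rate also among subjects transfused in the 8 weeks before enrollment, and state which date enrollment is.

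**Cost.** RFS, DOR and DOCR are text edits. TI is a changed definition, but the planned transfusion log already covers 8 weeks before enrollment to end of treatment. No visits, samples or subjects are added. There are two downsides: longer-treated subjects have more chances to qualify for TI, and the baseline-transfused denominator is smaller.
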